The effect of progressive balance exercise on postural sway – a 4 week randomized controlled trial

Today most fracture prevention measures targets the bone and osteoporosis. However, only about 20% of individuals with fractures have osteoporosis and at least 90% of all fractures are caused by a fall. Therefore, the present project builds on previous findings from our group identifying postural sway as an important risk factor for falls and aims to intervene against this risk factor in a randomized controlled trial targeting subjects at the highest risk for falls.

Specific aims:

1. Examine whether four weeks progressive balance training can improve parameters of body sway in measurements of static standing balance
2. Investigate whether participants experience greater security to their own ability and less fear of future falls after 4 weeks of progressive balance training
3. Investigate how long a potential effect of progressive balance training may be noticeable on participants' experiences of greater security in their own ability and less fear of future falls
4. 3. Examine whether participation in balance training leads to reduced number of falls at follow-up after 6, 12 and 24 months

Background

Falls and fall-related injuries are major health concerns for elderly individuals; they cause functional decline and increased mortality, as well as incurring vast health care costs for society.¹⁻³ Occurrences and consequences of falls are expected to increase globally with the growing number of elderly individuals. Hence, the improved detection and prediction of potential fall risk markers are of individual and societal importance.

Falling can be the end result of intrinsic and extrinsic factors negatively affecting an individual's ability to maintain balance,⁴ which are often revealed during sequences of body movement.⁵ Balance can be both dynamically and statically measured, the latter involves having the individual in a stationary standing position, from which results researchers have proposed impaired postural stability as a risk factor for falling.^{6,7} However, evidence regarding the association of postural instability with prospective falls is limited, and population-based cohort studies in this field are scarce.⁸ Other shortcomings of previous studies include the use of retrospective study designs,⁹ which increase the risks of recall bias and the identification of risk factors as the result of falls.^{10,11}

Postural instability is preferably investigated using objective measures of posturography, the advantages of which over regular clinical assessments include the reduction of test performance variability and avoidance of subjective scoring systems.¹² Recently, researchers have analyzed the performance of the Wii Balance Board (WBB; Nintendo, Kyoto, Japan) in the measurement of postural instability; WBB-based assessment has shown excellent concurrent validity and the ability to complement existing fall assessments.^{13,14}

As of 2012, all 70-year olds in the Umeå municipality are invited to participate in the Healthy Ageing Initiative (HAI) study, which has currently enrolled more than 3000 participants.

Among other measurements, we include assessment of postural stability using a Wii Balance Board (WBB; Nintendo, Kyoto, Japan) device. With each participant in a quiet stance, balance trials consisting of 60-second eyes-open (EO) and eyes-closed (EC) trials are performed. Participants are instructed to maintain an upright position throughout the test, stand relaxed, and avoid any arm or head movement. The WBB measures total COP sway length, representing the sum of postural sway in the anteroposterior and mediolateral directions.

Preliminary results from our analysis of data consisting of 1900 70-year-old individuals revealed that participants with postural sway in the 5th quintile had almost twice the risk of

falling compared to the reference group, when the 1-year follow-up of prospective falls was performed.

Thus the aim of the present follow-up study is to investigate if we can reduce the increased postural sway of participants who have been identified as having abnormal balance values, based on previous measurements.

Project description

Study design

The present project is planned to be conducted as a 4-week randomized intervention study with a follow up time of 2 years.

Study population

Recruitment of individuals at high risk of falls from the Healthy Ageing Initiative

The Healthy Ageing Initiative (HAI) is an ongoing population based project aiming to reduce risk factors for non-communicable diseases (NCD) by risk factor evaluation and increased physical activity.¹⁵ In short, HAI is inviting all 70 year olds in Umeå municipality to a health examination where traditional and potential novel risk factors for diabetes, CVD and fractures are investigated. These include objective measures of physical activity, blood pressure, blood-glucose, objective measured abdominal fat mass and ectopic fat, bone density and other features of bone quality, cognitive function, balance, walking ability, and different life style factors. At the second visit, all participants are informed about the results of tests performed and gets advice with a focus on physical activity, aiming at decreasing the risk of future diabetes, CVD and fractures. The counseling with focus on physical activity is based on motivational interviewing (MI) which is a directive patient-centered counseling style to help the participants to explore and resolve their ambivalence about behavior change. They are

contacted at 6 months and 12 months per telephone for follow up and are contacted for an in-clinic follow up after 5 years.

Participants in HAI identified as being in the highest quartile of measures of postural sway, indicating poor balance and high fall risk, are invited to participate by telephone contact, and will upon agreement be randomized into either the intervention group or control group.

Participants will after the initial contact also receive written information about the study. We aim to recruit 90 individuals from the existing HAI study cohort

Study protocol

Please see figure 1 for figure of study protocol.

Intervention protocol

Group 1

Twenty participants are randomised into the intervention group. The intervention group will perform group training sessions a week, consisting of 30 minutes of training for 4 weeks.

Group 2

Forty participants are randomised into the control group and receive a health consultation that highlights the importance of physical activity and balance exercise according to standard practice within the HAI project. They are asked to return after 4 weeks for follow up.

Follow up

After 4 weeks, the groups are followed up with the same measures that are used in the Healthy Ageing Initiative that contains objective and functional balance tests, tests of muscle strength and a validated questionnaire on fear-of-falling and physical activity. Both groups will be offered the specific program for balance training post measurements, with instructions that it can be performed in the home setting according to the same principles offered to the intervention group. The groups are followed up after 6 and 12 months through 70-years-health checks on prospective falls and levels of physical activity.

Methods used for baseline and follow up

Measurements of postural stability

Postural stability is assessed using a Wii Balance Board (WBB) device (Nintendo, Kyoto, Japan) labeled “Nintendo RVL-WBC-01”, with a nominal sampling frequency of 100 Hz. The equipment is linked to a PC via Bluetooth connection “E1310E(00**”, using drivers labeled

intervention
three supervised
minutes of balance

“Manage Library for Nintendo’s Wiimote v1.7.00 by Brian Peek”. The software was designed in Microsoft C# by [name], Umeå University. The equipment’s power supply has been exchanged from battery to USB power. The validity and reliability of the WBB has been evaluated elsewhere, showing excellent conformation to other laboratory balance equipment, with mean differences in center of pressure (COP) variance ranging between 0.3 to 3%.¹³

Participants are examined during quiet stance involving trials of eyes open (EO) and eyes closed (EC) for 60 seconds each. Participants are instructed to maintain an upright position throughout the test and stand relaxed, while avoiding any arm or head movements. The WBB measures total COP sway length, representing the sum of postural sway in anteroposterior and

Measurements of physical activity and capacity

Participants will be asked to complete the short form of the International Physical Activity Questionnaire (IPAQ),¹⁷ an instrument designed to estimate activity levels among adult populations in domains including: 1) leisure time PA, 2) domestic and gardening activities, 3) work-related PA and 4) transport-related PA. Individuals are asked to recollect the duration of activities (walking, moderate- and vigorous- intensity PA) during the last 7 days in each domain. Questionnaire responses are used to calculate MET-min data in accordance with IPAQ guidelines.¹⁷

Participants will also be asked to perform the Time-Up-and-Go (TUG) test,¹⁸ commonly used by clinicians to assess lower leg muscle strength, gait performance and overall functional mobility in elderly individuals. Testing involves participants rising unaided from an armchair and walking forward 3 meters until they reach a selected line on the floor, at which point they turn and come back to a seated position. Research nurses provides instructions and measures total testing time using a stopwatch. The TUG test have previously demonstrated good inter-

rater reliability (ICC=0.99).¹⁸ Testing of isometric muscle strength involves using a hydraulic hand dynamometer (Jamar, Patterson Medical, Warrenville, IL, USA) to measure participant's maximum grip strength in the non-dominant hand. Participants will be instructed to keep the arm angled at 90° and maintain the elbow in proximity to the waist during the test. The maximum value out of 2 consecutive attempts is subsequently recorded.

Measurement of Confidence in Balance Ability and Fear-of-Falling

Participants will also be asked to report confidence in balance ability and fear of falling. This will be accomplished through two questionnaires. The Falls Efficacy Scale International (FES-I) measures fear of falling and is comprised of 16 questions on a scale from 1-4.¹⁹ The Original Falls Efficacy Scale (FES) is also included and measures confidence in balance ability, formed by answering 13 questions on a scale from 1-10.²⁰

Anthropometric measures

Anthropometric data will be obtained using a scale (HL 120; Avery Berkel, Fairmont, MN, USA) to measure weight, and a gauge (Holtain Limited; Crymych, Dyfed, UK) to measure height.

Statistical analysis plan

Descriptive data will be presented as means + standard deviations and the Student's t-test will be used to analyze statistical differences between variables. Categorical variables are investigated using chi-squared tests. Potential differences between intervention and control group will be analyzed using paired and independent t-tests. All analyses will be performed with SPSS version 24 (IBM Corp, Armonk, NY, USA) and Stata version 13.1 (StataCorp, College Station, Texas, USA).

Ethical considerations

Importance

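### Aim 1 has two sway conditions, and the plan does not say which condition, which comparison or what significance level decides it

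*Combined protocol and SAP*

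**What the plan says.** - **Aim.** The first item under Specific aims is to "Examine whether four weeks progressive balance training can improve parameters of body sway in measurements of static standing balance". The title and the end of the Background also put sway first.
- **Metric.** Under Measurements of postural stability: "The WBB measures total COP sway length, representing the sum of postural sway in anteroposterior and" (the extracted text breaks off there; the Background gives the same definition in full). Only this one sway metric is described.
- **Conditions.** The same section says: "Participants are examined during quiet stance involving trials of eyes open (EO) and eyes closed (EC) for 60 seconds each". Neither condition is given priority. The entry rule under Study population does not settle it: it refers to the top quartile of sway measures, in the plural, and names no condition.
- **Tests.** The Statistical analysis plan says that "the Student's t-test will be used to analyze statistical differences between variables", that categorical variables get chi-squared tests, and: "Potential differences between intervention and control group will be analyzed using paired and independent t-tests".
- **Other week-4 outcomes.** IPAQ, TUG ("Participants will also be asked to perform the Time-Up-and-Go (TUG) test"), grip strength ("measure participant's maximum grip strength in the non-dominant hand"), and FES-I and FES for fear of falling and confidence ("This will be accomplished through two questionnaires").

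The plan labels no outcome as primary. It gives no significance level, sidedness, testing order or adjustment, and does not say whether sway is judged on the 4-week value or on the change from baseline.

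**The concern.** With two sway conditions and no rule linking them to a conclusion, a significant result in either one could be reported as meeting aim 1. Two chances at the nominal level give an error rate above that level.

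The choice of comparison is also open. The analysis section lists paired tests next to independent tests as ways to examine differences between the groups. A paired test within the intervention arm does not compare arms. Participants are selected for high sway, so if the selection measurement also serves as baseline, some improvement is expected in both arms from regression to the mean. A significant paired result could then be read as a training effect.

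If the condition and the comparison are settled only after the data are seen, a reader cannot tell a planned choice from a choice of the better result.

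**Working it through.** The documents give no alpha, power, SD, effect size or sample-size calculation, so there is no figure of the plan's own to reproduce.

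**Inputs from the documents**
- Sway conditions: 2 (EO, EC).
- Week-4 outcomes: 7 (EO, EC, IPAQ, TUG, grip, FES-I, FES).
- Arms under Intervention protocol: 20 intervention, 40 control.

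**Assumptions**
- Two-sided 5% per test.
- No true effect on any outcome.
- Correlations between outcomes as shown; the documents give none.

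**Step 1: aim 1, between-arm tests only.** For independent tests, the chance of at least one false positive is 1 − 0.95^k. With k = 2: 1 − 0.9025 = 0.0975. For correlated tests it is 1 − P(|Z1| < 1.96 and |Z2| < 1.96), with Z1 and Z2 bivariate normal.

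| EO–EC correlation (assumed) | At least one false positive, two-sided |
|---|---|
| 0 | 9.8% |
| 0.5 | 9.1% |
| 0.7 | 8.3% |
| 0.9 | 7.0% |

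Errors in favour of training are about half of these. With independence, 1 − 0.975² = 0.0494, or 4.9%.

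**Step 2: the seven week-4 outcomes, if any one were read as success.** Independent: 1 − 0.95^7 = 0.302. Simulated t-tests at 20 versus 40 with equal correlations give about 23% at 0.5 and 18% at 0.7. In favour of training only, with independence: 1 − 0.975^7 = 0.162.

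**Step 3: paired tests also read as evidence for aim 1.** This makes three tests per condition (between arms and within each arm), six in all. Simulation with no mean change in either arm gives about 21% at EO–EC correlation 0, 20% at 0.5 and 19% at 0.7.

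**Step 4: regression to the mean in the paired test.** This applies only if the selection measurement is the baseline, which the documents do not settle. For 20 people from the top quartile and no treatment effect, the paired test is significant in about 24%, 42% and 60% of simulated trials at assumed test–retest correlations of 0.9, 0.8 and 0.7.

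**Step 5: error rate and power after the change.** With Holm over EO and EC, the smaller p-value is compared with 0.025 and, if that succeeds, the larger with 0.05. The overall error is at most 5% whatever the correlation; with independence and no effect on either it is 1 − 0.975² = 4.94%. From the non-central t distribution with 58 degrees of freedom, the difference detectable with 80% power at 20:40 is 0.780 SD at alpha 0.05 and 0.863 SD at alpha 0.025.

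**The case against.** The strongest reply is that the plan is clearer than this suggests. The title, the first aim and the end of the Background all put sway first, and one metric is named. EO and EC are two trials of that metric on one device and may well be highly correlated, in which case the error is nearer 7% than 10%. About half of it would point against training, and reporting both conditions would make the issue visible. All of this stands, and it keeps the point narrow. It does not say which condition or which comparison decides the aim.

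A reader might infer more, in three ways the documents do not support:

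- **That every outcome is tested at 5%.** No significance level appears and no test is assigned to each outcome. The 5% is an assumption made here to give the gap a size.
- **That a false positive is more likely than not.** Between-arm tests do not reach that. Even ten independent tests (the seven plus falls at three times) give 1 − 0.95^10 = 40%, and it takes 14 to pass one half (51%). For the seven outcomes, one half is passed only if the paired tests in both arms also count and correlations are low: about 58% at correlation 0 and 46% at 0.5.
- **That any of the seven outcomes could formally carry the trial.** TUG, grip strength and IPAQ belong to no specific aim, and nothing says that a result on them would count as success. Whether separate aims should share one error rate is itself debatable, so the 18% to 30% range is conditional.

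**Conclusion.** The concern holds in a limited form. Domain and metric are clear; the deciding condition, the deciding comparison and the significance level are not stated.

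At an assumed two-sided 5% per test, the two between-arm sway tests carry a false-positive risk of about 7% to 10% instead of 5%, depending on the EO–EC correlation, which the documents do not give. About half of that favours training. The risk is about 18% to 30% for the seven week-4 outcomes only if any one of them were read as success.

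This is moderate inflation. It does not show that the trial cannot answer aim 1 or that a positive result would probably be false. The open role of the paired tests matters at least as much, since at the correlations compared, counting them takes the aim 1 figure to about 19% to 21% even before any regression to the mean. The gap is worth closing because a short rule restores 5% at little cost.

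**What to change.** Before outcome data are seen, state in the SAP:

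1. The primary analysis is the between-arm comparison of total COP sway length at 4 weeks, at two-sided 5% overall, and whether it uses the 4-week value or the change from baseline.
2. EO and EC are both tested with Holm's method, or one condition is named outright as the single primary. Pointing to the condition used for entry would not work, because the entry rule names none.
3. Paired within-arm tests are descriptive and do not decide the aim.
4. All other outcomes, including fear of falling and falls, are secondary. They are reported with estimates and 95% intervals and do not substitute for the primary result.

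**Cost.** Only SAP wording changes. Naming one condition costs no power. Holm over both raises the difference detectable with 80% power at 20:40 from 0.78 SD to at most 0.86 SD. Those figures rest on the stated arms, which total 60, while the recruitment target under Study population is 90. The two must be reconciled and the detectable differences recalculated if the arm sizes change.

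### Aim 3 asks how long the gain in confidence and fear of falling lasts, but the plan names no later FES/FES-I measurement and only t-tests, which could make a constant effect look faded

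*Combined protocol and SAP*

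**What the plan says.** Aim 3 (Specific aims) is to "Investigate how long a potential effect of progressive balance training may be noticeable" on participants' confidence and fear of falling. It gives no time points and does not define noticeable.

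The section on confidence and fear of falling names two instruments, FES-I (16 items scored 1 to 4) and FES (13 items scored 1 to 10): "Participants will also be asked to report confidence in balance ability and fear of falling". It stands under a heading covering baseline and follow-up, without saying which follow-up contacts are meant.

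The Follow up section places the fear-of-falling questionnaire at 4 weeks, among "tests of muscle strength and a validated questionnaire on fear-of-falling and physical activity". Of later contacts it says: "The groups are followed up after 6 and 12 months through 70-years-health checks on prospective falls and levels of physical activity". Study design describes a "4-week randomized intervention study with a follow up time of 2 years", and the aim on falls names 24 months, but the Follow up section gives no content for a 24-month contact. It also states that "Both groups will be offered the specific program for balance training post measurements".

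The Statistical analysis plan says "Potential differences between intervention and control group will be analyzed using paired and independent t-tests". The only other test is for categories: "Categorical variables are investigated using chi-squared tests". It mentions no repeated-measures model, arm-by-time contrast, confidence interval or missing-data method.

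On size, Study population gives a target of 90, while the Intervention protocol assigns 20 to intervention and 40 to control, which makes 60.

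**The concern.** Duration of effect is a question about how the arm difference changes over time. An independent t-test at one contact asks whether the arms differ there. A paired t-test within an arm asks whether that arm changed. Neither, used that way, estimates whether the arm difference has changed. If the reader is left with a p-value at each contact, it is easy to take the last significant contact as the duration of the effect. That point depends on how many people remain and on chance, as well as on the effect itself.

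Two further problems come before the choice of test. Without FES and FES-I after week 4 there is nothing with which to answer aim 3. And once both arms are offered the programme, a smaller arm difference no longer has only one explanation. At stake is a report that the benefit wore off when it did not, or an aim that cannot be reported at all.

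**Working it through.** **1. What is scheduled, as far as the visible text shows**

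| Contact | FES / FES-I | Source |
|---|---|---|
| Baseline | Yes | Methods used for baseline and follow up |
| 4 weeks | Fear-of-falling questionnaire | Follow up |
| 6 and 12 months | Not listed; falls and physical activity only | Follow up |
| 24 months | Content not described | Specific aims (falls); Study design |

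Figure 1 is not available here and may list more.

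**2. The plan's own figure.** There is none to reproduce. The documents give no significance level, power, effect size, SD or drop-out rate. Everything below rests on assumed inputs: two-sided 5% level, constant effect of 0.5 or 0.8 SD, random loss equal in both arms, and correlation of 0.5 to 0.7 between contacts. Arms are 20 v 40 as stated, or 45 v 45 as one reading of the 90.

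**3. Power of a single t-test as numbers shrink.** Power ≈ Φ(d / √(1/n₁ + 1/n₂) − 1.96).

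- 20 v 40, no loss: √(1/20 + 1/40) = 0.274. At 0.8 SD, 0.8/0.274 = 2.92 and power is Φ(0.96) = 83%. At 0.5 SD it is 45%.
- 14 v 28 (30% loss): √(1/14 + 1/28) = 0.327. At 0.8 SD, 0.8/0.327 = 2.44 and power is Φ(0.48) = 69%. At 0.5 SD it is 33%.
- 45 v 45, then 31 v 31, at 0.8 SD: 97%, then 88%.

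The noncentral t gives values 0.3 to 2.5 points lower.

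**4. How often a constant effect appears to be lost.** Simulated chance that a result significant at week 4 is non-significant at a later contact, with the true effect unchanged. Ranges cover correlations 0.5 to 0.7.

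| Arms | Effect | No loss | 20% loss | 30% loss | 40% loss |
|---|---|---|---|---|---|
| 20 v 40 | 0.8 SD | 10–13% | 20–23% | 25–30% | 34–36% |
| 20 v 40 | 0.5 SD | 29–38% | 41–48% | 48–55% | 54–60% |
| 45 v 45 | 0.8 SD | 2–3% | 7–8% | 11–12% | 16–17% |
| 45 v 45 | 0.5 SD | 18–24% | 30–34% | 37–42% | 44–47% |

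The 48–55% entry spans two simulations: 48–52% with 3,000 runs per scenario and 49–55% with 20,000.

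With four contacts, losses of 0, 10, 20 and 30%, 20 v 40 and 0.8 SD, about 37 to 46% of trials significant at week 4 have at least one later non-significant contact.

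**5. The direct test.** Testing the change in arm difference from week 4 to the last contact declares a change in about 5% of these trials. That is simply its nominal level. The cost is low power. In SD units its standard error is √(2(1 − ρ)) × √(1/n₁ + 1/n₂). At 14 v 28:

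- ρ = 0.5: 1.000 × 0.327 = 0.327. The 95% CI half-width is 1.96 × 0.327 = 0.64 SD. A true halving from 0.8 to 0.4 SD is detected with probability Φ(0.4/0.327 − 1.96) = 23%.
- ρ = 0.7: 0.775 × 0.327 = 0.254. The half-width is 0.50 SD, and the probability is Φ(0.4/0.254 − 1.96) = 35%.

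So the direct test removes the excess of false fading, but will often leave the question open.

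**The case against.** Several stronger readings are tempting, and the documents do not support them.

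- **That the trial will judge duration by whether p stays below 0.05.** No decision rule is written, so only that it could be judged so. A t-test on each person's change from week 4 would test the change in arm difference directly, and the SAP wording does not exclude it. The plan is unspecific rather than committed to the faulty reading.
- **That drop-out is the cause.** The no-loss column shows that low power alone produces the same pattern, and the documents give no drop-out rate.
- **That FES and FES-I are definitely not collected after week 4.** The Follow up section does not list them, but figure 1 cannot be seen, and the methods heading refers to follow-up in general.
- **That 25 to 30% is a property of this trial.** It belongs to one set of assumptions. With 45 v 45 at 0.8 SD the corresponding figure is 11 to 12%; with 20 v 40 at 0.5 SD it is about half.
- **That a mixed model by itself answers aim 3.** It cannot supply scores that were never collected. It also cannot separate fading from controls catching up once both arms are offered the programme.

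All five limits stand. They leave the core intact: aim 3 needs later scores, and the SAP states no method that estimates how the arm difference changes across contacts.

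**Conclusion.** The point holds in limited form and should be addressed before analysis. Aim 3 is a duration question with no later FES/FES-I contact in the visible text, no definition of duration, no stated longitudinal or missing-data analysis, and a comparison group that is offered the programme after week 4. If later scores are compared by separate t-tests, an unchanged effect could be misread as fading. On the assumptions above, the chance of this by the last contact, given significance at week 4, runs from about one in nine (45 v 45, 0.8 SD, 30% loss) to about one in two (20 v 40, 0.5 SD, 30% loss). It is not negligible at 20 v 40 even with complete data. The point concerns aim 3, not the postural sway aim.

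**What to change.** 1. State at which of the existing follow-up contacts FES-I and FES are collected, and confirm that both are collected at week 4, where the text mentions one questionnaire.
2. For each scale, fit one linear mixed model to all available post-baseline scores, with baseline score, arm, contact and arm × contact, allowing for correlation within a person. Report the arm difference with its 95% CI at each contact.
3. Answer aim 3 with the arm difference at the later contact minus the arm difference at week 4, with its 95% CI. Say in advance that a wide interval means that fading can be neither shown nor ruled out.
4. Record uptake of the programme after week 4, above all among controls. State that a narrowing difference may reflect controls improving, and report within-arm change from week 4 beside the contrast, as description.
5. Reconcile the 20 and 40 with the stated 90.

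The cost is mainly SAP wording; SPSS and Stata, both already named, can fit the model. The downsides are a missing-at-random assumption that must be stated, low power for the contrast at this size, and a small questionnaire burden at later contacts.

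### Falls are an aim, but the plan lists no baseline fall history and no adjusted falls analysis; adding both is a cheap, minor gain in precision

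*Combined protocol and SAP*

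**What the plan says.** - **Outcome.** Under Specific aims, the last item is to "Examine whether participation in balance training leads to reduced number of falls at follow-up after 6, 12 and 24 months". The Follow up section names two of these time points: "The groups are followed up after 6 and 12 months through 70-years-health checks on prospective falls and levels of physical activity".
- **Baseline.** The section headed "Methods used for baseline and follow up" covers sway on the balance board, IPAQ, Timed Up and Go (TUG), grip strength, FES-I, FES, weight and height. Previous falls are not among them.
- **Analysis.** The Statistical analysis plan names paired and independent t-tests and chi-squared tests. It names no covariate, stratification factor or count model for any outcome.
- **Numbers.** "Twenty participants are randomised into the intervention group" and "Forty participants are randomised into the control group". The Study population section gives a different total: "We aim to recruit 90 individuals from the existing HAI study cohort".
- **Existing falls data.** The Background reports that people in the top fifth of sway had close to double the risk of "falling compared to the reference group, when the 1-year follow-up of prospective falls was performed". HAI participants are also "contacted at 6 months and 12 months per telephone for follow up". The trial recruits from this cohort.

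**The concern.** Falls tend to recur in the same people, so a person's earlier falls are a plausible predictor of later ones. In arms of 20 and 40, fall-prone people can easily be split unevenly by chance. The plan neither lists the variable that would show this nor provides an analysis that would use it. A reader of the falls result will ask whether the arms had similar fall histories, and the plan does not ensure an answer.

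Timing matters too. A history recorded before randomisation cannot be affected by allocation. One recalled after the training period could be. What is at stake is precision and interpretability on a secondary aim. The trial's main question, postural sway, is not affected.

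**Working it through.** **Inputs from the documents.** Arms of 20 and 40. The documents give no fall rate, dispersion, effect size, alpha or power for falls, so there is no falls calculation to reproduce. The one figure that can be checked is the total: 20 + 40 = 60, not the 90 stated.

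**Assumed inputs.** Prior-faller share 20 to 40%; 0.3 to 0.8 falls per person-year; gamma frailty shape k of 0.5 to 1 (dispersion 1/k, that is 1 to 2), stable over time; prior fallers at 1.5 to 3 times the risk or rate of others; two-sided alpha 0.05; no dropout.

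**1. Chance imbalance.** SD of the arm difference in prior-faller share = sqrt(p(1 − p)(1/20 + 1/40)). At p = 0.30 this is sqrt(0.21 × 0.075) = 0.125. Exact binomial probabilities for 20 v 40:

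| Prior fallers | gap ≥ 15 points | gap ≥ 20 points |
|---|---|---|
| 20% | 21% | 9% |
| 30% | 27% | 13.5% |
| 40% | 31% | 16% |

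At 30%, a gap of at least 25 points has probability 5.8%. If 90 were enrolled, a gap of at least 15 points at 30% would have probability 13% (45:45) or 17% (30:60).

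**2. What a 15-point gap does.** Take 40% v 25% prior fallers and no treatment effect. If prior fallers fall at twice the rate, the crude rate ratio becomes (0.60 + 0.40 × 2)/(0.75 + 0.25 × 2) = 1.40/1.25 = 1.12. At three times the rate it is 1.80/1.50 = 1.20.

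**3. Variance removed by a prior-year count.** With a shared gamma frailty and two one-year windows at rate μ, the correlation is r = (μ²/k)/(μ + μ²/k) = μ/(μ + k).
- μ = 0.3, k = 1: r = 0.23, r² = 5%.
- μ = 0.8, k = 0.5: r = 0.62, r² = 38%.
- μ = 0.5: r² = 11% (k = 1) to 25% (k = 0.5).

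r² applies to a linear count and is the large-sample ceiling in this model. Simulation at 20 v 40, using log(1 + prior falls) by least squares, gives about 5 to 34% at 12 months overall and 10 to 23% at 0.5 falls a year. At that same rate it is about 5 to 17% at 6 months and 14 to 32% at 24 months.

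**4. What that does to power.** Use a negative binomial model with 30% prior fallers (history as yes/no), mean 0.5 to 0.8 falls per person and dispersion 1 to 2. One case worked through: mean 0.5, dispersion 1, rate ratio of prior fallers 2.
- Group means: 0.5/1.3 = 0.385 and 0.769.
- Crude variance of the log rate ratio: (0.781 + 0.031)/0.25 × 0.075 = 0.244, SE 0.494.
- Adjusted: information per person = 0.7 × 0.385/1.385 + 0.3 × 0.769/1.769 = 0.325. Variance = 0.075/0.325 = 0.231, SE 0.480.
- Variance falls by 5%. Power for a halved fall rate goes from 28.9% to 30.2%.

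Over the whole grid, variance falls by 5 to 8% (rate ratio 2) or 12 to 18% (rate ratio 3). Power moves from 20–36% to 23–38%, a gain of 1 to 5 points.

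**5. Proportion falling.** For 30% v 15%, power is 22.2% unadjusted and 25.9% if history explains 15% of the variance. Reaching 80% unadjusted would need about 186 controls and 93 intervention participants.

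**The case against.** The case for leaving this alone has four parts.

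- **The documents are silent.** A reader might infer that no fall history is taken. The text does not say so: the list of HAI examinations is introduced as a partial one, figure 1 is not available in the text, and part of the methods text is garbled. Only the narrower statement stands, that no fall history is listed and none is used.
- **Adjustment is not impossible.** A reader might infer that an imbalance could never be corrected. That goes too far. Earlier HAI falls data could be linked for some recruits, and sway, TUG and FES-I are measured at baseline. But the plan provides for none of these. Sway is probably a weak adjuster here, because all recruits come from the top quarter of its distribution.
- **HAI data may not fit, and recall is imperfect.** The documents do not say how long after the HAI visit people enter the trial, so the recorded year may not be the year before randomisation. The Background itself criticises retrospective designs for recall bias. Both points stand as limits on quality. Recall error in a covariate asked before allocation cannot depend on arm, so it weakens the gain without biasing the comparison.
- **The gain is small.** This stands. Chance imbalance under randomisation is already counted in the standard error. A reader might hope that adjustment would make the falls comparison informative, and step 4 of the working shows that it would not. The aim also has larger, separate gaps: no falls model is specified, both arms are offered the programme after the 4-week measurements, and 24-month falls appear in the aim but not in the Follow up section.

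**Conclusion.** The point holds as a minor, cheap improvement. Falls are a stated aim, no fall history is listed at baseline, and no adjusted analysis is planned, so the plan does not provide for adjustment on a likely predictor. At 20 v 40 and an assumed 30% prior fallers, roughly one randomisation in four would leave a gap of 15 points or more. Adjusting for log(1 + prior falls) would remove about 5 to 34% of the variance at 12 months, less at 6 months and more at 24.

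Every rate behind these figures is assumed, and the upper end needs strong, stable clustering of falls within people. If prior fallers have only 1.5 times the risk, a yes/no history is worth about 1 to 3% in effective sample size; at three times the risk it is worth 15 to 28%. The documents do not support a claim of bias, nor a claim that the covariate would give adequate power.

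**What to change.** 1. Before randomisation, record the number of falls in the previous 12 months for every participant. Use the HAI falls follow-up where its dates cover that year, and one question otherwise. Add the item to the listed baseline measures.
2. In the Statistical analysis plan, specify the between-arm falls analysis for the last aim as a count model, for example negative binomial with a follow-up-time offset, and prespecify log(1 + prior falls) as a covariate. Recording the history without this second step would gain nothing in the comparison.
3. State that the falls comparison is exploratory at this size, and reconcile the target of 90 with arms of 20 and 40.

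The cost is one question or a data extract, plus one model term. The downside is that prior falls will be recalled rather than prospectively recorded for some participants, but equally so in both arms because the question comes before allocation.
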